APPENDIX F. TEST OF UNDERSTANDING

RV460/WRAIR #2672**Test of Understanding**

True	False	1.	Volunteers in this vaccine study will be protected against HIV.
True	False	2.	You will need to come to the clinic for 26 scheduled visits (including this one) over the next 2 years.
True	False	3.	The vaccines in this study will give you HIV.
True	False	4.	One purpose of this study is to determine if these vaccines are safe to administer to humans.
True	False	5.	Participants in this study will need to avoid engaging in activities that may expose them to HIV infection.
True	False	6.	You may take other experimental (test) products while you are taking part in this study.
True	False	7.	You may withdraw from the study at any time if you choose or your participation may be stopped if the study team decides it is in your best interest.
True	False	8.	Women are asked to not become pregnant while in the study.
True	False	9.	A participant in this study may experience side effects after vaccination.
True	False	10.	Because the vaccines may turn some of the standard tests for HIV infection positive, some people may incorrectly think that the study participants are infected with HIV (false-positive).

RV460/WRAIR #2672**Answer Key**

False	1.
True	2.
False	3.
True	4.
True	5.
False	6.
True	7.
True	8.
True	9.
True	10.

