4.2 ELIGIBILITY CRITERIA

4.2.1 INCLUSION CRITERIA

1. Healthy, male and female participant aged 18 to 40 years and available for 26 months
2. Must be at low risk for HIV infection per investigator assessment and using the study risk assessment tool.
3. Must be able to understand and complete the informed consent process.
4. Must be capable of reading English or Kiswahili.
5. Must agree to a home visit.
6. Willing to have photo or fingerprint taken for identification purposes.
7. Must complete a Test of Understanding (TOU) before enrollment. Must answer 9 out of 10 questions correctly, with a maximum of three attempts.
8. Must be in good general health without a clinically significant medical history.
9. HIV-uninfected per diagnostic algorithm within 45 days of enrollment.
10. Laboratory values:
 - **Hemoglobin:**
12.5-18.1 g/dL men
11.0-16.1 g/dL women
 - **White Cell Count:**
2.7-7.7 $\times 10^3$ cells/ μ L men
3.0-9.1 $\times 10^3$ cells/ μ L women
 - **Platelets:**
125-370 10^3 cells/ μ L men
125-444 10^3 cells/ μ L women
- **ALT and AST:** ≤ 1.25 institutional upper limit of the reference range
Creatinine: ≤ 1.25 institutional upper limit of the reference range
- **Urinalysis:** (dipstick) for blood and protein less than 1+ and negative glucose

Female-Specific Criteria:

11. Negative urine pregnancy test for women at screening, the day of each vaccination, and before any invasive procedure.
12. Already using and commits to continued use of an adequate birth control method for 45 days before to the first vaccine/placebo vaccination and for at least 90 days after the final vaccine/placebo vaccination. Adequate birth control is defined as follows: Contraceptive medications delivered orally, intramuscularly, vaginally, or implanted, underneath the skin, surgical methods (hysterectomy or bilateral tubal ligation), condoms with spermicide, diaphragms, intrauterine device (IUD), vasectomy in a monogamous partner, or abstinence.

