4.2.2 EXCLUSION CRITERIA

A history of:

1. Three or more sexual partners in the previous 24 weeks
2. Commercial sex work
3. Non-adherence to condom use in the absence of a long-term monogamous relationship
4. Intravenous drug use in the previous year.
5. A sexually transmitted infection in the previous 24 weeks
6. Is not a sexually active MSM or a transgender person in the past 6 months.
7. Asplenia: any condition resulting in the absence of a functional spleen
8. Bleeding disorder diagnosed by a medical doctor (e.g., factor deficiency, coagulopathy, or platelet disorder requiring special precautions)
9. Breastfeeding or pregnant (positive pregnancy test) women or planning to become pregnant during the window between study enrollment and three months after the last vaccination visit.
10. Any past, ongoing, or in remission history of treated or untreated autoimmune disease.
11. Has known active Hepatitis B virus infection (or positive HBsAg).
12. Has known active Hepatitis C infection
13. History of anaphylaxis or other serious adverse reaction to vaccines or allergies or reactions likely to be exacerbated by any component of the vaccine and placebo, including antibiotics or excipients
14. Absolute Neutrophil Count (ANC):
$$<1.0 \times 10^3 \text{ cells}/\mu\text{L}$$
15. Participant has received any of the following substances:

- Chronic use of therapies that may modify immune response, such as intravenous (IV) immune globulin and systemic corticosteroids (in doses of >20 mg/day prednisone equivalent for periods exceeding 10 days)
- The following exceptions are permitted and will not exclude study participation:
 - use of corticosteroid nasal spray for rhinitis,
 - topical corticosteroids for an acute uncomplicated dermatitis; or
 - A short course (10 days or less, or a single injection) of corticosteroid for a non-chronic condition (based on investigator clinical judgment) at least 2 weeks before enrollment.

16. Blood products within 120 days before HIV screening
17. Immunoglobulins within 30 days before HIV screening
18. Any experimental vaccine containing an adjuvant other than aluminum or an adjuvant not approved by the FDA or European Medicines Agency (EMA) as part of a licensed vaccine.
19. CERVARIX vaccine against HPV (containing AS04)
20. Receipt of any investigational HIV vaccine, investigational research agents or vaccine within 30 days before enrollment.
21. Anti-tuberculosis prophylaxis or therapy during the past 90 days before enrollment

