5.5 STUDY VISITS

Participants will have up to 26 clinic visits. The active study phase will last a total of 105 weeks, which will include the time of the first screening visit through the final clinic study visit. In addition, participants will be contacted once per week for 3 weeks (3 phone contacts) following the 105 week active study phase. At these contacts, staff will collect the information listed below.

- Confirmation of vital status; if deceased, attempt to learn cause and date of death;
- If participant is alive, record the participant's responses to questions regarding any occurrence of the following events since the last study contact:
 - Life-threatening adverse experiences;
 - Persistent or significant disability/incapacity;
 - Hospitalizations and reasons;
 - New diagnosis of HIV infection; and
 - Pregnancies and outcomes, including congenital anomalies/birth defects

All such events will be recorded, and adverse events other than HIV infection will be assessed for relationship to study product(s). Clinic visits will only be required if HIV confirmatory testing is necessary; however, a clinic visit may be arranged for other reasons.

Evaluation of the safety of the study vaccines is outlined in the schedule of evaluations (SOE) and will include laboratory studies, medical history, physical assessment by clinicians, and participant self-assessment recorded on a 7-day diary card. Additional study visits may be required if, in the investigator's opinion, any lab value warrants repeating. The first vaccination visit could take up to 6 hours, but the other vaccination visits take about 4 hours each. Most other follow-up clinic visits will usually take about 2 hours.

Total blood volume drawn from each participant will not exceed the US Department of Defense (DoD), American Association of Blood Banks (AABB) and FDA guidelines of 450 mL in an eight-week period. If a participant is anemic, each visit's blood volume will be reviewed, and the blood drawn for research may be reduced or not drawn at all, depending on the severity of anemia.

Table 4: Visit Procedures

Clinic visit activities

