9.2.1.4 Unknown Risks

There may be other serious risks that are not known with the study vaccines.

Participants may believe that this vaccine provides HIV protection, and therefore practice riskier behavior. They will receive extensive counseling throughout the study to address this potential problem. It is not known if the vaccines increase or decrease the chance of becoming HIV infected when exposed or if becoming HIV infected the person's disease course progresses faster to AIDS.

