APPENDIX G. PARTICIPANT VISIT SCHEDULE

RV460/WRAIR #2672**Appendix G**
Participant Visit Schedule

Visit No.	Visit Day	Clinic visit activities	Optional Procedures	Approx. Time	Reimbursement
Screening	-45 to -3 days	Screening: Briefing & contact information, informed consents, test of understanding, medical history, vital signs, complete physical exam, 1 TBSP blood draw for: HIV test, hepatitis B and C, syphilis, general health, urine pregnancy test for women, urine test (dipstick) for blood and protein	-Pap smear for women who agree to vaginal secretion collection	4-5 Hours	1000 Ksh
1	0	Vaccination 1*: Enrollment & randomize, exam & eligibility review, vaccination or placebo, examine injection site 30-60 minutes post-injection, receive diary card, urine pregnancy test for women, 12 TBSP blood draw for: research tests & HIV	-Mucosal secretion collection	5 - 6 Hours	1000 Ksh (+1000 Ksh for each mucosal secretion collection)
Phone call or Clinic Visit 24-48 hours After Vaccination					1000 Ksh
2	3	Follow Up: exam & symptom review, review diary card, 2 TBSP blood draw for: research tests. Bring diary card.		2 Hours	1000 Ksh
3	7	Follow Up: exam & symptom review, review & collect diary card, 2 TBSP blood draw for: research tests. Bring diary card.		3 Hours	1000 Ksh
4	14	Follow Up: exam & symptom review, 5 TBSP blood draw for: general health & research tests		2 Hours	1000 Ksh
5	28	Vaccination 2*: Exam & eligibility review, vaccination or placebo, examine injection site 30-60 minutes post-injection, receive diary card, urine pregnancy test for women, 2 TBSP blood draw for: research tests		4 Hours	1000 Ksh
Phone call or Clinic Visit 24-48 hours After Vaccination					1000 Ksh

Visit No.	Visit Day	Clinic visit activities	Optional Procedures	Approx. Time	Reimbursement
6	35	Follow Up: exam & symptom review, Review diary card, 2 TBSP blood draw for: research tests. Bring diary card.		2 Hours	1000 Ksh
7	42	Follow Up: exam & symptom review, 4 TBSP blood draw for: research tests and general health. Urine pregnancy test for women that elect for optional procedure(s). Bring diary card.	-Mucosal Secretion collection	4 - 5 hours	1000 Ksh (+1000 Ksh for each mucosal secretion collection)
8	84	Vaccination 3*: Exam & eligibility review, vaccination or placebo, examine injection site 30-60 minutes post-injection, receive diary card, urine pregnancy test for women, 3 TBSP blood draw for: research tests		4 Hours	1000 Ksh

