19	392	Vaccination 6*: Exam & eligibility review, vaccination or placebo, examine injection site 30-60 minutes post-injection, receive diary card, urine pregnancy test for women, 3 TBSP blood draw for: research tests		4 Hours	1000 Ksh
Phone call or Clinic Visit 24-48 hours After Vaccination					1000 Ksh
20	395	Follow Up: exam & symptom review, review diary card, 2 TBSP blood draw for: research tests. Bring diary card.		2 Hours	1000 Ksh
21	399	Follow Up: exam & symptom review, review & collect diary card, 5 TBSP blood draw for: research tests & HIV. Bring diary card.		3 Hours	1000 Ksh

Visit No.	Visit Day	Clinic visit activities	Optional Procedures	Approx. Time	Reimbursement
22	406	Follow Up: exam & symptom review, 11 TBSP blood draw for: general health & HIV & research tests. Urine pregnancy test for women that elect for optional procedure(s).	-Mucosal secretion collection -Lymph node biopsy	5 - 6 Hours	1000 Ksh (+1000 Ksh for each mucosal secretion collection & 5000 Ksh for lymph node biopsy)
Return in 1 week if lymph node biopsy was performed					
23	476	Follow Up: exam & symptom review, 9 TBSP blood draw for: research tests. Urine pregnancy test for women that elect for optional procedure(s).	-Mucosal secretion collection	4 - 5 Hours	1000 Ksh (+1000 Ksh for each mucosal secretion collection)
24	560	Follow Up: exam & symptom review, 9 TBSP blood draw for: research tests & HIV. Urine pregnancy test for women that elect for optional procedure(s).	-Mucosal secretion collection	4 - 5 Hours	1000 Ksh (+1000 Ksh for each mucosal secretion collection)
25	728	Follow Up: exam & symptom review, 9 TBSP blood draw for: research tests & HIV. Urine pregnancy test for women that elect for optional procedure(s).	-Mucosal secretion collection	4 - 5 Hours	1000 Ksh (+1000 Ksh for each mucosal secretion collection)
26 Exit	735	Final visit: exam & symptom review, 4 TBSP blood draw for: research tests		2 Hours	1000Ksh

Reimbursement

Study visits: 1000 Ksh

Unscheduled visits: Up to 500 Ksh, at the discretion of the study doctor

Mucosal collection: 1000 Ksh per each collection

Lymph node biopsy: 5000 Ksh

Transportation: Up to 3000 Ksh, at the discretion of the study doctor

* A study vaccination may be given outside your vaccination window if the protocol safety review team (PSRT) permits.

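### Item 2 of the Test of Understanding is keyed True for 26 clinic visits counting screening, but Appendices A and G list 27; section 5.5 carries the same count and starts the 105 weeks at screening

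*Protocol*

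**What the plan says.** Appendix F is a ten-item true/false test. Item 2 states "You will need to come to the clinic for 26 scheduled visits (including this one) over the next 2 years", and the answer key marks it True. The test is scored for inclusion criterion 7 in section 4.2.1: "Must answer 9 out of 10 questions correctly, with a maximum of three attempts". Section 5.2 makes a volunteer ineligible only when the third attempt has also failed.

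The first row of Appendix G shows when the test is taken: "Screening: Briefing & contact information, informed consents, test of understanding, medical history". The rows that follow are numbered 1 to 26. The last, visit 26 on day 735, is described as "Final visit: exam & symptom review, 4 TBSP blood draw for: research tests". Appendix A has the same layout, with a column S1 followed by columns 1 to 26.

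Section 5.5 says "Participants will have up to 26 clinic visits" and describes the 105-week active phase as starting at the first screening visit. The Precis (Study Duration) instead counts the 105 weeks of clinic follow-up from enrollment and randomization, and Appendix A places week 105 at day 735 from Day 0.

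Item 8, also keyed True, says "Women are asked to not become pregnant while in the study". Inclusion criterion 12 asks for contraception for a minimum of 90 days after the final vaccination. Exclusion criterion 9 covers women "planning to become pregnant during the window between study enrollment and three months after the last vaccination visit".

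**The concern.** A comprehension test should reward the answer that the protocol supports. Item 2 does the opposite for anyone who reads the visit schedule, because a correct count earns a wrong mark. The pass mark leaves room for only one error, so a volunteer with the right count has no margin left for a genuine slip, while a volunteer with the wrong count still has one.

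This is more than a stray figure in background text, because the key decides an eligibility criterion. Section 5.5 repeats the count, so the protocol body and its own schedule disagree on how many clinic visits there are and on when the 105 weeks begin.

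**Working it through.** **Visit count.** Inputs: the visit columns of Appendix A, the visit rows of Appendix G, and the timing of the test (Appendix G and section 5.2, both at screening). The words in item 2 about the present visit therefore refer to screening.

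- Appendix A: 1 (S1) + 26 (visits 1 to 26) = 27.
- Appendix G: 1 (screening) + 26 (visits 1 to 26) = 27.
- The plan's figure: 27 − 1 = 26, reproduced only when screening is left out.

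The count covers numbered scheduled clinic visits only. It leaves out the contacts 24 to 48 hours after each vaccination, for which telephone is the default (Table 4), the return visits after an optional biopsy, and the three closing calls.

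**The 105 weeks.** Inputs: exit visit on day 735 and a screening window of day −45 to day −3 (Appendix A).

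- From enrollment: 735 / 7 = 105.0 weeks, as in the Precis.
- From screening: (735 + 3) / 7 = 105.4 weeks to (735 + 45) / 7 = 111.4 weeks.

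The figure of 105 weeks is exact from enrollment. Counting from screening, as section 5.5 does, adds 3 to 45 days.

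**Effect on the score.** Pass mark: at least 9 of 10.

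- Item 2 answered False (by the schedule), all else as keyed: 10 − 1 = 9, a pass.
- Item 2 answered False plus one genuine error: 10 − 2 = 8, which fails that attempt.
- Item 2 answered True plus the same genuine error: 10 − 1 = 9, a pass.

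The keying error costs one mark in ten. It changes the result of an attempt only when there is exactly one other error.

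**Item 8.** The last vaccination is at day 392 (week 56). The stated minimum ends at 392 + 90 = day 482, or days 475 to 489 with the ±7-day window. From day 482 there are 735 − 482 = 253 days to the exit visit and 756 − 482 = 274 days to week 108. Item 8 does not say where in that span its request ends.

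**The case against.** The strongest reply is that this is an off-by-one count that excludes nobody. By itself it leaves a score of 9/10, which passes, and a failed attempt can be repeated twice. Section 5.5 also says 26, so a True answer agrees with one part of the protocol. The test follows signed consent, and section 5.2 has volunteers receive a visit schedule with their copy of the consent form. The documents therefore do not show that anyone was misinformed about the burden. All of this stands and limits the size of the point. It does not make the key right: the schedule contradicts it, and section 5.5 shares the error.

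A reader might also infer more than the documents support:

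- *That a volunteer who answers items 2 and 8 by the protocol scores 8/10 and fails.* This requires item 8 to be false, and it is not. The 90 days are a minimum, women are asked to avoid pregnancy through much of the study, and True is the natural answer. The 253 or 274 days measure an open end point and not a misstatement.
- *That the true burden is 36 contacts (27 + 6 + 3), or that two years is false.* Item 2 is about coming to the clinic, and the added nine contacts are wholly or by default telephone calls. Clinic visits end at day 735, which is 735 / 365.25 = 2.01 years from enrollment, so two years is fair rounding. The 26 months in inclusion criterion 1 is still the better figure to match.
- *That the pass mark is wrong because a volunteer who misses only item 1, on protection against HIV, scores 9/10.* Section 9.2.1.4 does recognize the risk: "Participants may believe that this vaccine provides HIV protection, and therefore practice riskier behavior". It also promises counseling throughout the study to address it. No part of the protocol is contradicted by a mark without a compulsory item, so this is a design preference.

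**Conclusion.** The point holds as a small, definite error in an operative place. Item 2 is one visit short (26 stated, 27 scheduled) and is keyed True in the test that scores inclusion criterion 7. Its cost is one mark in ten, which is the whole error allowance for a volunteer who counts correctly, but it cannot by itself fail an attempt or make anyone ineligible. Section 5.5 has the same count and starts the 105 weeks at the wrong point. Item 8 is imprecise about its end point and is not shown to be wrong.

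This rests on reading the present visit in item 2 as screening, which both section 5.2 and Appendix G support, and on taking each numbered entry in Appendices A and G as one clinic visit. The consent form is not among the pages available, so its wording on visits and pregnancy could not be compared. No endpoint, analysis or safety rule is affected.

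**What to change.** 1. Appendix F, item 2: state 27 scheduled clinic visits including this one, or 26 after this one, with a duration consistent with the 26 months in inclusion criterion 1. The key can then stay True.
2. Section 5.5: state 27 clinic visits including screening, and 105 weeks counted from enrollment, in line with the Precis and Appendices A and G.
3. Appendix F, item 8: reconcile its end point with inclusion criterion 12, exclusion criterion 9 and section 9.2.1.6, so that the test and the eligibility text name the same period.
4. Optional: the team may consider making a correct answer to item 1 a condition of passing, within the same mark and three attempts. Some volunteers might then need another attempt.

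Items 1 to 3 change one appendix page and one paragraph and can go in with the next amendment. They have no effect on design, sample size or analysis.

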APPENDIX G. PARTICIPANT VISIT SCHEDULE

RV460/WRAIR #2672**Appendix G**
Participant Visit Schedule

Visit No.	Visit Day	Clinic visit activities	Optional Procedures	Approx. Time	Reimbursement
Screening	-45 to -3 days	Screening: Briefing & contact information, informed consents, test of understanding, medical history, vital signs, complete physical exam, 1 TBSP blood draw for: HIV test, hepatitis B and C, syphilis, general health, urine pregnancy test for women, urine test (dipstick) for blood and protein	-Pap smear for women who agree to vaginal secretion collection	4-5 Hours	1000 Ksh
1	0	Vaccination 1*: Enrollment & randomize, exam & eligibility review, vaccination or placebo, examine injection site 30-60 minutes post-injection, receive diary card, urine pregnancy test for women, 12 TBSP blood draw for: research tests & HIV	-Mucosal secretion collection	5 - 6 Hours	1000 Ksh (+1000 Ksh for each mucosal secretion collection)
Phone call or Clinic Visit 24-48 hours After Vaccination					1000 Ksh
2	3	Follow Up: exam & symptom review, review diary card, 2 TBSP blood draw for: research tests. Bring diary card.		2 Hours	1000 Ksh
3	7	Follow Up: exam & symptom review, review & collect diary card, 2 TBSP blood draw for: research tests. Bring diary card.		3 Hours	1000 Ksh
4	14	Follow Up: exam & symptom review, 5 TBSP blood draw for: general health & research tests		2 Hours	1000 Ksh
5	28	Vaccination 2*: Exam & eligibility review, vaccination or placebo, examine injection site 30-60 minutes post-injection, receive diary card, urine pregnancy test for women, 2 TBSP blood draw for: research tests		4 Hours	1000 Ksh
Phone call or Clinic Visit 24-48 hours After Vaccination					1000 Ksh

Visit No.	Visit Day	Clinic visit activities	Optional Procedures	Approx. Time	Reimbursement
6	35	Follow Up: exam & symptom review, Review diary card, 2 TBSP blood draw for: research tests. Bring diary card.		2 Hours	1000 Ksh
7	42	Follow Up: exam & symptom review, 4 TBSP blood draw for: research tests and general health. Urine pregnancy test for women that elect for optional procedure(s). Bring diary card.	-Mucosal Secretion collection	4 - 5 hours	1000 Ksh (+1000 Ksh for each mucosal secretion collection)
8	84	Vaccination 3*: Exam & eligibility review, vaccination or placebo, examine injection site 30-60 minutes post-injection, receive diary card, urine pregnancy test for women, 3 TBSP blood draw for: research tests		4 Hours	1000 Ksh
Phone call or Clinic Visit 24-48 hours After Vaccination					1000 Ksh
9	87	Follow Up: exam & symptom review, review diary card, 2 TBSP blood draw for: research tests. Bring diary card.		2 Hours	1000 Ksh
10	91	Follow Up: exam & symptom review, review & collect diary card, 4 TBSP blood draw for: research tests. Bring diary card.		3 Hours	1000 Ksh
11	98	Follow Up: exam & symptom review, 9 TBSP blood draw for: general health, HIV & research tests. Urine pregnancy test for women that elect for optional procedure(s).	-Mucosal secretion collection -Lymph node biopsy	5 - 6 Hours	1000 Ksh (+1000 Ksh for each mucosal secretion collection & 5000 Ksh for lymph node biopsy)
Return in 1 week if lymph node biopsy was performed					
12	140	Vaccination 4*: Exam & eligibility review, vaccination or placebo, examine injection site 30-60 minutes post-injection, receive diary card, urine pregnancy test for women, 3 TBSP blood draw for: research tests		4 Hours	1000 Ksh
Phone call or Clinic Visit 24-48 hours After Vaccination					1000 Ksh
13	143	Follow Up: exam & symptom review, review diary card, 2		2 Hours	1000 Ksh

Visit No.	Visit Day	Clinic visit activities	Optional Procedures	Approx. Time	Reimbursement
		TBSP blood draw for: research tests. Bring diary card.			
14	147	Follow Up: exam & symptom review, review & collect diary card, 3 TBSP blood draw for: research tests. Bring diary card.		3 Hours	1000 Ksh
15	154	Follow Up: exam & symptom review, 9 TBSP blood draw for: general health, HIV & research tests. Urine pregnancy test for women that elect for optional procedure(s).	-Mucosal secretion collection	4 - 5 hours	1000 Ksh (+1000 Ksh for each mucosal secretion collection)
16	224	Vaccination 5*: Exam & eligibility review, vaccination or placebo, examine injection site 30-60 minutes post-injection, receive diary card, urine pregnancy test for women, blood draw for: 2 TBSP research tests		4 hours	1000 Ksh
Phone call or Clinic Visit 24-48 hours After Vaccination					1000 Ksh
17	231	Follow Up: exam & symptom review, review diary card, 3 TBSP blood draw for: research tests. Bring diary card.		2 Hours	1000 Ksh
18	238	Follow Up: exam & symptom review, 9 TBSP blood draw for: research tests, general health & HIV. Bring diary card. Urine pregnancy test for women that elect for optional procedure(s).	-Mucosal secretion collection	4 - 5 Hours	1000 Ksh (+1000 Ksh for each mucosal secretion collection)
19	392	Vaccination 6*: Exam & eligibility review, vaccination or placebo, examine injection site 30-60 minutes post-injection, receive diary card, urine pregnancy test for women, 3 TBSP blood draw for: research tests		4 Hours	1000 Ksh
Phone call or Clinic Visit 24-48 hours After Vaccination					1000 Ksh
20	395	Follow Up: exam & symptom review, review diary card, 2 TBSP blood draw for: research tests. Bring diary card.		2 Hours	1000 Ksh
21	399	Follow Up: exam & symptom review, review & collect diary card, 5 TBSP blood draw for: research tests & HIV. Bring diary card.		3 Hours	1000 Ksh

Visit No.	Visit Day	Clinic visit activities	Optional Procedures	Approx. Time	Reimbursement
22	406	Follow Up: exam & symptom review, 11 TBSP blood draw for: general health & HIV & research tests. Urine pregnancy test for women that elect for optional procedure(s).	-Mucosal secretion collection -Lymph node biopsy	5 - 6 Hours	1000 Ksh (+1000 Ksh for each mucosal secretion collection & 5000 Ksh for lymph node biopsy)
Return in 1 week if lymph node biopsy was performed					
23	476	Follow Up: exam & symptom review, 9 TBSP blood draw for: research tests. Urine pregnancy test for women that elect for optional procedure(s).	-Mucosal secretion collection	4 - 5 Hours	1000 Ksh (+1000 Ksh for each mucosal secretion collection)
24	560	Follow Up: exam & symptom review, 9 TBSP blood draw for: research tests & HIV. Urine pregnancy test for women that elect for optional procedure(s).	-Mucosal secretion collection	4 - 5 Hours	1000 Ksh (+1000 Ksh for each mucosal secretion collection)
25	728	Follow Up: exam & symptom review, 9 TBSP blood draw for: research tests & HIV. Urine pregnancy test for women that elect for optional procedure(s).	-Mucosal secretion collection	4 - 5 Hours	1000 Ksh (+1000 Ksh for each mucosal secretion collection)
26 Exit	735	Final visit: exam & symptom review, 4 TBSP blood draw for: research tests		2 Hours	1000Ksh

Reimbursement

Study visits: 1000 Ksh

Unscheduled visits: Up to 500 Ksh, at the discretion of the study doctor

Mucosal collection: 1000 Ksh per each collection

Lymph node biopsy: 5000 Ksh

Transportation: Up to 3000 Ksh, at the discretion of the study doctor

* A study vaccination may be given outside your vaccination window if the protocol safety review team (PSRT) permits.

